### 7.5.3 Pneumonitis

Management guidelines for patients experiencing pneumonitis are as follows:

- Grade 1 pneumonitis - No specific therapy required; close monitoring of lung function and imaging.
- Grade 2 pneumonitis - Hold MGD007 and MGA012

- Consider corticosteroids: 1 to 2 mg/kg of oral prednisone or equivalent, per day divided twice daily.
- Taper over 4 weeks as clinically indicated.
- Resume MGD007 and MGA012 administration at the next scheduled dose if pneumonitis resolves to  $\leq$  Grade 1 within 3 days with or without treatment.
- Grade 3 and 4 pneumonitis - discontinue MGD007 and MGA012.
  - Hospitalize the patient.
  - Initiate maximal supportive care including IV corticosteroids, suggest methylprednisolone at 2 to 4 mg/kg/day divided twice daily. Higher doses may be used in consultation with the Sponsor's Medical Monitor.
  - If no response to corticosteroid therapy is observed within 3 to 5 days, consider adding immune suppression therapy (i.e., infliximab, etc.).
  - MGA012 should be permanently discontinued
  - Upon resolution of the pneumonitis to Grade 1 or less in severity, resumption of MGD007 monotherapy may be considered on a case-by-case basis in consultation with the Sponsor.

#### 7.5.4 Dermatologic Toxicity

Management guidelines for patients experiencing dermatologic toxicity are as follows:

- Grade 1 or 2 skin reactions
  - Symptomatic treatment with low-dose topical corticosteroids (betamethasone 0.1% or hydrocortisone 1%) or antihistamines (diphenhydramine).
  - Persistent Grade 1 or 2 rash should be managed with higher dose topical corticosteroids and/or oral prednisone (1 to 2 mg/kg/day) if there is not improvement with topical therapies or the rash is associated with other dermal toxicities such as pruritus.
- Grade 3 skin reactions Hold MGD007 and MGA012
  - Initiate oral corticosteroids (oral prednisone 1 to 2 mg/kg/day).
  - MGD007 and MGA012 may be restarted at the next scheduled dosing if symptoms resolve to  $\leq$  Grade 2 within 14 days.
  - Grade 3 skin toxicity that does not resolve to  $\leq$  Grade 2 within 14 days of initiation of oral corticosteroids requires permanent discontinuation of study drugs (MGD007 and MGA012).
- Grade 4 skin reactions - Discontinue MGA012 and MGD007

- Initiate oral corticosteroids (oral prednisone 1 to 2 mg/kg/day).
- Consideration should be given to start IV corticosteroids (methylprednisolone 1 to 2 mg/kg/day) for Grade 4 dermatologic toxicities with tapering on resolution to < Grade 2 over 30 days.
- MGD007 and MGA012 should be permanently discontinued.

### 7.5.5 Nephritis

Management guidelines for patients experiencing nephritis are as follows:

- Grade 1 nephritis - No specific therapy required; close monitoring of renal function.
- Grade 2 nephritis - Hold MGD007 and MGA012.
  - Consider nephrology consultation and renal biopsy to confirm interstitial nephritis.
  - Begin corticosteroids: 1 to 2 mg/kg of oral prednisone or equivalent, per day divided twice daily. Taper over 4 weeks as clinically indicated.
  - Resume MGD007 and MGA012 administration at next scheduled dose if:
    - Nephritis resolves to  $\leq$  Grade 1 within 14 days with or without treatment.
- Grade 3 and 4 nephritis - Permanently discontinue MGD007 and MGA012.
  - Consider hospitalization, nephrology consultation, and renal biopsy to confirm interstitial nephritis.
  - Begin corticosteroids: 2 to 4 mg/kg of oral or IV prednisolone or equivalent per day divided twice daily. Taper over 4 weeks as clinically indicated.

### 7.5.6 Immune-mediated Hypophysitis

Management guidelines for patients experiencing hypophysitis are as follows:

- Grade 1 hypophysitis - No specific therapy required.
- Grade  $\geq 2$  hypophysitis - Hold MGD007 and MGA012
  - Consult endocrinologist.
  - Consider hospitalization.
  - Consider short course of high dose IV corticosteroids: e.g., methylprednisolone 2-4 mg/kg IV (or equivalent) divided twice daily.
  - Initiate hormonal replacement as indicated.

- MGD007 and MGA012 treatment may be resumed as allowed by protocol when:
  - Endocrinopathy is controlled with appropriate replacement therapy.
  - Corticosteroid dose reduced to  $\leq 10$  mg prednisone or equivalent per day.
- Brain MRI recommended.
- Grade 4 hypophysitis - MGD007 and MGA012 should be permanently discontinued.

### 7.5.7 Thyroid Toxicity

Thyroid disorders may occur at any time during treatment. Monitor patients for changes in thyroid function per protocol and as indicated based on clinical evaluation and for clinical signs and symptoms of thyroid disorders. Isolated hypothyroidism may generally be managed with replacement therapy without treatment interruption and without corticosteroids; treatment management algorithms for patients experiencing endocrinopathy, and a suggested treatment guideline for hyperthyroidism is described below:

- Grade 1 hyperthyroidism - No specific therapy required.
- Grade 2 hyperthyroidism - Hold MGD007 and MGA012.
  - Consider starting oral corticosteroid therapy.
  - Short course of corticosteroid such as methylprednisolone 1 to 2 mg/kg IV (or equivalent) divided twice daily.
  - Resume MGD007 and MGA012 if corticosteroid dose is reduced to  $\leq 10$  mg prednisone or equivalent per day and stable on hormone replacement therapy (if necessary).
- Grade 3 or 4 hyperthyroidism - Hold MGD007 and MGA012.
  - Consider hospitalization and consulting endocrinologist.
  - Begin IV corticosteroids such as methylprednisolone 2 to 4 mg/kg IV (or equivalent) divided twice daily.
  - Initiate hormonal replacement as necessary.
  - Consider restarting MGD007 and MGA012 with complete resolution or stable on hormone replacement therapy within 14 days and if corticosteroid dose is reduced to  $\leq 10$  mg prednisone or equivalent per day.

**PLEASE NOTE FOR EVENTS DESCRIBED IN SECTIONS 7.2 - 7.5:** For patients who experience drug-related DLT that occurs prior to the initiation of MGA012, or for selected immune-related AEs clearly related to the mechanism of action of MGA012, continued

treatment of patients with either MGA012 or MGD007 monotherapy, respectively, may be considered selectively, on a case-by-case basis, in consultation with the Sponsor.

## 8 CONCOMITANT THERAPY AND RESTRICTIONS

### 8.1 Concomitant Therapy

All concomitant medications, including prophylactic pre-infusion medications, and blood products administered during the patient's participation in the study until the end of treatment visit must be recorded in the source document and on the electronic Case Report Form (eCRF). All changes in infusions, including interruptions and their duration as well as reductions in rate and duration, must be recorded.

#### 8.1.1 Prohibited Therapy

The following rules concerning concurrent treatment(s) will apply in this study:

- Any other anti-neoplastic therapies including but not limited to chemotherapy or other small molecules, biologics, or radiotherapy are not allowed.
  - For patients who require palliative radiotherapy (i.e., cumulative dose less than 30 Gy, limited field of distribution) for reasons other than disease progression, therapy may be interrupted for up to 4 weeks. Palliative radiotherapy may not be given concurrently with the study drug. Treatment with palliative therapy should be initiated at least 24 hours after receiving study drug, and reinitiation can begin 2 weeks after the completion of palliative radiotherapy. If palliative radiotherapy fields overlap tumor lesions that are designated target lesions, the patient may continue on study, but will no longer be evaluable for objective response from the time palliative radiotherapy is initiated.
- Patients may not receive other investigational drugs during the period of study participation.
- The use of other immunosuppressive agents is prohibited unless they are being used to treat an AE.
- Prophylactic use of granulocyte colony stimulating factor, granulocyte-macrophage colony stimulating factor, or other growth factors is prohibited.
- Patients should not receive vaccination with any live virus vaccine during the study and for 120 days following a patient's last dose of MGA012 or of MGD007. Inactivated annual influenza vaccination is allowed.
- Because both MGD007 and MGA012 employs a mechanism of action dependent upon the engagement of T lymphocytes, the use of corticosteroids should be limited to the extent possible. Chronic doses of corticosteroids in excess of 10 mg daily of prednisone or equivalent is prohibited other than for the management of drug-related adverse experiences. Steroids may be employed in the treatment of suspected MGD007- and MGA012-associated autoimmune AEs in consultation with the Sponsor. Specifically, use of budesonide is required with MGD007 dosing per schedule outlined in [Section 7.1](#).

- Use of biphosphonates or RANK-L inhibitors is prohibited.
- Concomitant use of CYP450 substrates with a narrow therapeutic index should be avoided.

## **8.1.2 Permitted Therapies**

Patients may receive the following concurrent therapy:

- Antiemetics, antidiarrheals, anticholinergics, antispasmodics, antipyretics, antihistamines, analgesics, antibiotics and other antimicrobials, histamine receptor antagonists or proton pump inhibitors, and other medications intended to treat symptoms or signs of disease.
- Transfusions such as red blood cells and platelets are permitted to treat symptoms or signs of anemia or thrombocytopenia.

## **8.2 Restrictions**

### **8.2.1 Fluid and Food Intake**

There are no requirements for fasting and no restrictions for fluid and food intake by the patients during the study, although it is recommended that, to the extent possible, patients have a fluid intake of  $\geq 2$  liters on days associated with PK sampling, and that electrocardiograms be obtained pre-meal.

### **8.2.2 Patient Activity Restrictions**

There are no restrictions on patient activities and no requirement for patient confinement during the study.

## **9 STUDY PROCEDURES**

This section provides a general description of the procedures and assessments associated with this study. The timing of the study procedures is presented in [Appendix 1](#).

### **9.1 Informed Consent**

The Investigator is responsible for ensuring that the patient or his/her legal representative provides informed consent prior to performing any study-related assessments, evaluations, or procedures that are not part of standard-of-care for the patient's disease. Informed consent for this study must be provided by signing an Institutional Review Board (IRB)/Independent Ethics Committee (IEC)-approved informed consent document (Consent for Study Participation). A copy of the relevant signed informed consent document must be provided to the patient and the original maintained according to institutional procedures. The patient's medical records will include documentation of the informed consent process.

### **9.2 Screening Period**

Patients may receive the first dose up to 28 days from signing the informed consent. This period is defined as the screening period. At the screening visit, patients will enter the study upon signing the informed consent document. No screening activities outside of usual standard-of-care should be performed prior to obtaining informed consent from the patient. Only those patients who meet all inclusion/exclusion criteria specified in [Section 5](#) will be entered into this study.

### **9.3 Registration**

Only those patients who meet all inclusion/exclusion criteria specified in [Section 5](#) will be entered into this study.

Once the patient has been determined to be eligible for enrollment into the study, the patient must be registered with MacroGenics. The following information should be provided during registration:

- Date of signed informed consent
- Planned date of first administration

Instructions for the registration process are provided in the Study Procedures Manual.

### **9.4 Medical History**

A complete medical history should be obtained during the screening visit. All concurrent medical conditions in the last 60 days and any significant past medical conditions (e.g., hospitalizations, surgeries, chronic conditions, prior cancer history, etc.) should be

collected. Any untoward event that occurs prior to the first dose of study drug should be recorded as medical history and not as an AE unless it is due to a protocol-related procedure.

## **9.5 Prior and Concomitant Medications**

All concomitant medications and blood products administered during screening and the patient's participation in the study until the End of Treatment Visit must be recorded in the source document and on the eCRF.

Prior courses of systemic cancer therapy (e.g., chemotherapy, immunotherapy, etc.) will be documented in the medical records and on the eCRF.

## **9.6 Physical Examination**

The Investigator will perform physical examination of all patients; the examination will be conducted as specified in [Appendix 1](#). Full physical examination will be performed at screening and at the End of treatment visit, and it will include height (screening only), weight, and examination of skin, HEENT (head, eyes, ears, nose, and throat), lymph nodes, heart, chest, lungs, abdomen, extremities, and neurologic system. All other physical examinations will be directed physical examinations based on patient symptoms, tumor location, and as clinically indicated.

### **9.6.1 Vital Signs**

Vital signs include temperature, pulse, blood pressure, and respiratory rate and are obtained as specified in [Appendix 1](#). It is recommended vital signs are obtained in a seated, semi-recumbent, or supine position after an appropriate rest.

## **9.7 ECOG Performance Status**

ECOG performance status should be measured as specified in [Appendix 1](#) and [Appendix 4](#).

## **9.8 Clinical Laboratory Tests**

Blood and urine samples will be collected at the times specified in [Appendix 1](#). Hematology, chemistry, pregnancy, urinalysis, coagulation time, and endocrine evaluation tests will be performed locally. Safety laboratory tests should be performed and reviewed before study drug administration.

### **9.8.1 Central Laboratory Assays**

Clinical laboratory tests to be performed are presented in [Appendix 2](#). There are no clinical laboratory tests (see [Appendix 2](#)) being analyzed at a central laboratory for this study.

Other laboratory tests (e.g., PK, anti-drug antibody [ADA] assays [[Appendix 3](#)]) will be analyzed at Sponsor-specified central laboratories. Additional details on collection,

processing, storage, and shipping of central laboratory samples will be provided in the Laboratory Manual.

### **9.8.2 Pharmacokinetics**

Blood samples for MGD007 and MGA012 PK will be collected at the time points shown in [Appendix 3](#). Blood samples will be collected from the arm contralateral to the site of IV infusion. If an indwelling catheter is used, the fluid in the catheter will be removed and discarded prior to the collection of blood sample for PK assessment.

Actual date and time of the start and end of infusions and PK sample collection will be recorded on the eCRFs.

### **9.8.3 Pharmacodynamics/Biomarkers**

Procedures for the acquisition, handling, and processing of pharmacodynamic biomarker specimens will be provided in the Laboratory Manual. These tests will be collected according to [Appendix 3](#). Samples are to be obtained at the time points specified in the Time and Events Schedule and the PK, immunogenicity, and pharmacodynamic biomarkers blood sample schedule for MGD007 and MGA012 ([Appendix 1](#) and [Appendix 3](#), respectively).

### **9.8.4 Sample Collection, Storage, and Shipping**

Details on laboratory specimen processing, storage, and shipping will be provided in the Laboratory Manual.

## **9.9 Radiographic, CT, or MRI Assessments**

Baseline tumor imaging consists of a CT/MRI scan for all patients. The subsequent tumor assessments on treatment should use the same imaging modality as that for the baseline assessment; for subsequent imaging timepoints see [Appendix 1](#).

A CT or MRI scan of the brain will be performed in cases in which it is clinically indicated (e.g., suspicion of brain metastases) and repeat brain scans will be performed only if the screening brain scan was positive, or as clinically indicated.

## **9.10 Electrocardiography**

Twelve-lead electrocardiograms will be obtained according to the Time and Events Schedules ([Appendix 1](#)) in order to evaluate the potential cardiac effect, including QTc interval prolongation. There are no requirements for fasting and no restrictions for fluid and food intake by the patients during the study, although it is recommended that, to the extent possible, ECGs be obtained pre-meal.

To account for intrinsic variability, all ECGs should be obtained in triplicate (3 ECGs per time point at approximately 1-minute intervals). Central interpretation of ECGs will be used for data analysis purposes.

Actual times of the ECG assessments will be recorded on the eCRFs.

## 9.11 End of Treatment Visit

A list of evaluations to be performed for the EOTV is provided in [Appendix 1](#); a CT or MRI Scan should be performed during the EOTV, unless a previous scan was performed < 28 days of the EOTV. Criteria for triggering the End of Treatment visit are specified in [Section 5.4](#).

The End of Treatment Visit should be performed after the patient has met off-study criteria. This visit should occur no later than 30 days since the last study dose and before any subsequent anti-cancer treatment. If EOTV < 30 days since the last study dose, the site should contact the patient for safety follow-up no later than 30 days after the last study dose (see [Section 12](#)). It is recognized that certain patients (such as those experiencing progression of disease) may be cared for in facilities other than the participating study site, may proceed to receive other cancer therapy, and/or may elect not to return to the study site. Therefore, this visit is considered optional, but should be carried out whenever possible. All required procedures and tests should be performed if a visit is performed.

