**Table 6 Summary Statistics of First Dose (C1D1) Pharmacokinetic Parameters for MGA012 in Study CP-MGA012-01**

MGA012 Dose (mg/kg)	PK Parameters				
	$C_{max}$ (ng/mL)	$AUC_{(INF)}$ (ng•h/mL)	CL (mL/h/kg)	$V_{ss}$ (mL/kg)	$t_{1/2}$ (h)
	GeoMean (%CV)	GeoMean (%CV)	Mean (SD)	Mean (SD)	Mean (SD)
1 (N = 3)	14.9 (37)	3359 (27)	0.304 (0.077)	87.2 (12.1)	216.8 (45.9)
3 (N = 18)	73.1 (36)	15352 (37)	0.200 (0.070)	84.4 (37.8)	401.5 (346.0)
10 (N = 10)	227.7 (22)	59515 (30)	0.169 (0.050)	86.4 (21.0)	422.3 (167.9)
Overall (N = 28 a )	NR	NR	0.189 (0.072)	85.1 (30.9)	408.9 (282.6)

a For Overall, N = 28 because CL,  $V_{ss}$ , and  $t_{1/2}$  appear to be comparable between the 3 and 10 mg/kg.

Abbreviations:  $AUC_{(INF)}$  = area under the serum concentration time curve from time zero extrapolated to infinite time; C1D1 = Cycle 1 Day 1;  $C_{max}$  = maximum observed serum concentration; CL = total body clearance; CV = coefficient of variation; GeoMean = geometric mean; N = number of patients; NR = not reported; Q2W = once every 2 weeks; SD = standard deviation;  $t_{1/2}$  = serum terminal elimination half-life;  $V_{ss}$  = volume of distribution at steady-state

NOTE: For the 3 and 10 mg/kg dose groups, data from Q2W and Q4W treated patients were combined into a single group because the PK assessment was after the first dose.

Preliminary PK data from 31 patients, including 3 patients in Cohort 1 (1 mg/kg Q2W), 10 patients in Cohort 2a (3 mg/kg Q2W), 8 patients in Cohort 2b (3 mg/kg Q4W), 6 patients in Cohort 3a (10 mg/kg Q2W), and 4 patients in Cohort 3b (10 mg/kg Q4W), suggested that first dose MGA012  $C_{max}$  was dose proportional and  $AUC_{(INF)}$  increased in a greater than dose proportional manner over the dose range of 1 to 10 mg/kg IV. Mean (SD) parameter values for CL,  $V_{ss}$ , and  $t_{1/2}$  appear to be comparable between the 3 and 10 mg/kg doses. Excluding the 1 mg/kg dose, the overall (N = 28) mean CL,  $V_{ss}$ , and  $t_{1/2}$  values of MGA012 were 0.189 mL/h/kg, 85.1 mL/kg, and 408.9 h (~ 17 days), respectively. The half-life of MGA012 suggests that the drug is expected to attain steady-state conditions within 85 days and predicted accumulation for the Q2W and Q4W regimens is expected to be ~ 2 and ~ 1.5, respectively. The volume of distribution indicates that MGA012 distribution is > than blood volume, but < than extracellular fluid volume.

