## 7.5 Immune-Related Adverse Events

Blockade of immune checkpoints (PD-1, PD-L1 and CTLA-4) has been associated with several immune mediated adverse events that develop as a result of disruption of immune tolerance in normal tissues ([18](#), [36](#), [43](#)). These include but are not limited to pneumonitis, autoimmune hepatitis, glomerulonephritis, central neurotoxicity (encephalitis), peripheral neuromuscular toxicity, diarrhea or colitis (discussed in [Section 7.3](#)), hypophysitis, thyroiditis, or other autoimmune endocrinopathies (e.g., pancreatitis and diabetes), myocarditis, and Stevens Johnson Syndrome/Toxic Epidermal Necrolysis. These IrAEs can occur late and require a prolonged follow up. The occurrence of any of these may dictate interruption and potentially discontinuation of study drug administration pending further evaluation and reporting them to the Sponsor as AESIs. Most low-grade immune-related AEs (irAEs) can be managed symptomatically. Persistent low-grade or moderate toxicities may require treatment with corticosteroids or in refractory cases other immune suppressing agents such as

mycophenolate or infliximab. High-grade immune-related toxicities will, in almost all cases, require treatment with high-dose corticosteroids.

Temporary interruptions of the study drugs may be required in the event of treatment-related, immune-related toxicity. General guidelines for specific toxicity regarding dosing and treatment are provided below. All toxicities will be graded according to NCI CTCAE v4.03.

Patients who receive corticosteroid therapy for  $\geq 4$  weeks at a dose equivalent to  $\geq 20$  mg of prednisone per day, consideration should be given to implementation of antibiotic prophylaxis for opportunistic infections.

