## 9.12 Post-treatment Follow-Up Visits

The post-treatment follow-up period includes the following:

- Survival follow-up: approximately a 2-year period for each patient following the last dose of any study drug.
- During this time, patients will be followed via telephone or other electronic contact at 3-month intervals for follow-up of OS.
- Response status: will be collected every 3 months on all patients who discontinued from study treatment due to reasons other than PD, if they have not initiated any other cancer-directed therapy.

Post-treatment follow-up is performed until the end of study for each patient.

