## 12.2.2 Immediately Reportable Events

Immediately Reportable Events (IREs) are events that must be reported immediately to MacroGenics within 24 hours of the study site’s awareness of the event.

- SAEs
- Pregnancy in a study patient or partner of a study patient. [Note: If the female partner of a male patient becomes pregnant, the partner must be requested to complete a Pregnant Partner Consent Form so that pregnant partner, fetal and/or newborn information can be collected.] Upon confirmation of serum pregnancy testing, the patient will be followed for the outcome of pregnancy. All live newborns will be followed 6 months after the birth, and all necessary information will be collected to assess the effects of study drug on the newborn. If necessary, the follow-up period will be extended for the newborn.
- The following AESIs ([Section 12.2.4](#)):
  - $\geq$  Grade 3 IRRs or CRS
  - Grade 2 or greater immune-related AEs of the following: events of colitis, pneumonitis, hepatitis, Stevens-Johnson syndrome (SJS), and toxic epidermal necrolysis (TEN), myocarditis, nephritis, hypophysitis, and hypo/hyper-thyroidism which are considered immune-mediated events
  - Abnormal liver enzymes that meet the criteria for potential Hy’s law, which is defined as AST and/or ALT that is greater than  $3 \times$  ULN and total bilirubin that is greater than  $2 \times$  ULN and without any alternate etiology
  - Grade 2 or greater diarrhea associated with visible blood in the stool or melena
  - Any Grade 3 or greater diarrhea irrespective of evidence of GI bleeding
- Administration of a dose significantly greater (specifically, + 20% or higher) than the planned dose, and results in an event of clinical consequence.

- AEs leading to permanent discontinuation of study drug in an individual patient.
- Withdrawal of the patient from study drug administration for any reason other than disease progression.

In those cases, in which the IRE is considered related to study drug, the study drug may be discontinued, and the patient will continue participation in the study for observational safety and analysis (except for cases where the patient is withdrawn from the study by the Investigator or withdrew the consent). At any time after completion of the study, if an Investigator becomes aware of a serious adverse event that s/he suspects is related to study drug, the Investigator should report the event to MacroGenics Product Safety.

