#### **12.2.4 Protocol-specific Adverse Events of Special Interest**

Specific adverse events or groups of adverse events will be followed as part of standard safety monitoring activities by the Sponsor. The Sponsor will be notified of these events in a timely manner, regardless of seriousness (i.e., serious and non-serious adverse events).

- All infusion-related reactions or CRS events (Note:  $\geq$  Grade 3 IRRs or CRS events are additionally considered immediately reportable events) (see [Section 7.2](#))
- Grade 2 or greater Immune related AEs of the following: events of colitis, pneumonitis, hepatitis, Stevens-Johnson syndrome (SJS), and toxic epidermal necrolysis (TEN), myocarditis, nephritis, hypophysitis, and hypo/hyper-thyroidism which are considered immune-mediated events (see [Section 7.5](#))

- Abnormal liver enzymes that meet the criteria for potential Hy's law, which is defined as AST and/or ALT that is greater than  $3 \times$  ULN and total bilirubin that is greater than  $2 \times$  ULN and without any alternate etiology
- Grade 2 or greater diarrhea associated with visible blood in the stool or melena
- Any Grade 3 or greater diarrhea irrespective of evidence of GI bleeding

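### Protocol 9.11 sets only a latest day for the post-treatment safety contact and makes it depend on an optional visit, so the last AE enquiry can come before the 30-day AE window closes

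*Protocol*

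**What the plan says.** Protocol 9.11 places the EOTV at or before Day 30 after the last dose and ahead of any new anti-cancer treatment. If the visit is earlier than Day 30, "the site should contact the patient for safety follow-up no later than 30 days after the last study dose", with a pointer to Section 12. The same paragraph accepts that "certain patients (such as those experiencing progression of disease) may be cared for in facilities other than the participating study site" and concludes: "Therefore, this visit is considered optional, but should be carried out whenever possible".

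After that, 9.12 provides that "patients will be followed via telephone or other electronic contact at 3-month intervals for follow-up of OS". Response status is added for some patients. AEs are not listed.

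The AE window runs to the later of the EOTV or Day 30 in the synopsis, Section 12, Appendix 1 and SAP 5.2.1. Section 12.2.1 runs it to Day 30 but stops earlier if new systemic anti-cancer therapy begins. After Day 30, 12.2.3 asks only for serious AEs (SAEs) judged related to study drug or a protocol procedure. Appendix 1 marks AE assessment as continuous.

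**The concern.** A contact meant to close a 30-day window should fall on or after the last day of that window. Section 9.11 sets the limit the other way: any day up to Day 30 complies, and a call on Day 31 would be late. The call is also conditional on an EOTV having happened, so a patient who skips the optional visit gets no call under 9.11.

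The patients whom 9.11 expects to lose to other facilities are those with progression. They also fall outside one of the prompts for rapid reporting, because 12.2.2 lists "Withdrawal of the patient from study drug administration for any reason other than disease progression".

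What is at stake is complete ascertainment of late AEs. Safety is a primary objective in escalation and a secondary one in expansion. Section 7.5 says of immune-related AEs: "These IrAEs can occur late and require a prolonged follow up". Section 12.2.4 makes "Grade 2 or greater Immune related AEs of the following: events of colitis, pneumonitis, hepatitis" and others AEs of special interest (AESIs), and SAP 6.7.1 tabulates them. A late Grade 2 event that is not serious is the kind that may go unrecorded if nobody asks.

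**Working it through.** The plan gives no figure for this gap, so there is nothing to reproduce. The check is day arithmetic on the schedule.

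**1. EOTV before Day 30.** Uncovered days = 30 − day of last AE-directed contact. The contact days below are illustrative; 9.11 allows all of them.

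| Last contact (day after last dose) | Uncovered days | Share of window |
|---|---|---|
| 8 (for example, after an EOTV on Day 7) | 30 − 8 = 22 | 73% |
| 14 | 30 − 14 = 16 | 53% |
| 21 | 30 − 21 = 9 | 30% |
| 28 | 30 − 28 = 2 | 7% |
| 30 | 0 | 0% |

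Of the days that 9.11 permits, only Day 30 itself covers the whole window.

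**2. No EOTV, progression at the end-of-cycle scan.** Inputs from Appendix 1: last MGD007 dose of the cycle on Day 50 (±1); scan on Day 56 (±3).

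- Last dose to scan: 56 − 50 = 6 days. With visit windows, the shortest is 53 − 51 = 2 and the longest is 59 − 49 = 10.
- Window days left without a scheduled enquiry: 30 − 6 = 24, range 30 − 10 = 20 to 30 − 2 = 28.

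This assumes that AEs are asked about at the scan visit. If they are not, the gap runs from the last dose and is the full 30 days. It also assumes that the patient is still on weekly MGD007. Section 9.11 waives the EOTV scan when one was done within the previous 28 days, so imaging gives this patient no separate reason to return.

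**3. Is an enquiry scheduled anywhere else?**

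- 9.12 and the follow-up footnote to Appendix 1: survival and response status only.
- EOTV footnote to Appendix 1: repeats the Day 30 upper limit and does not mention the safety contact.
- Section 12: defines the window and the reporting duty, but sets no contact day.
- 5.3: repeated telephone attempts and a certified letter before a patient is declared lost to follow-up. These concern missed visits and are not an AE enquiry at the close of the window.

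None of these places schedules an AE enquiry on or after Day 30.

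**4. With a contact on Day 30 to 37 for everyone:** uncovered days = 0 for each patient reached.

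**The case against.** The best defence is that 9.11 should be read together with Section 12, to which it points. On that reading the call exists to close the 30-day window, and a Day 8 call misses its purpose. AE assessment is continuous in Appendix 1. Section 12.2.1 requires every AE to Day 30 to be reported, even one learned of later. Grade 2 or higher immune-related AESIs must be entered within 24 hours of awareness (12.2.2, Table 12). Related SAEs can be reported at any time. Patients carry a study card, and withdrawals for toxicity are reported within 24 hours. The Study Procedures Manual, which is not available here, may add steps for missed visits.

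Much of this stands. It shows that the reporting duty is complete and that the most important events are protected once known. It does not supply the enquiry. These duties operate on what the site learns, and 9.11 itself expects some patients to be cared for elsewhere.

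A reader might infer more than the documents support:

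- *That AEs after the last contact are not reportable.* They are, under 12.2.1.
- *That 24 lost days is typical.* It is one scenario. Patients with unconfirmed immune-related progression may stay on treatment (4.1, 11.1.1). For those who start new systemic therapy before Day 30, 12.2.1 closes the window earlier.
- *That the MGA012 half-life of about 17 days (Protocol 2.6.2.1) measures the risk in the uncovered days.* In the scan scenario the last MGA012 dose is on Day 43, a week before the last MGD007 dose, and Table 7 shows a faster fall from peak than the half-life alone suggests. Late onset and slow clearance bear on how long the window should be, which is a different question.
- *That the window definitions should be aligned by deleting the 12.2.1 early stop.* That would mean collecting AEs under new therapy, where attribution is confounded. It is a debatable trade-off and no part of this point.
- *That dose-limiting toxicity (DLT) decisions or efficacy are at risk.* The DLT period ends on Cycle 1 Day 42. Patients who receive under 75% of planned doses for unrelated reasons are replaced (4.1.1). Efficacy rests on scans and survival.

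**Conclusion.** The point holds as a limited gap in scheduled ascertainment. A compliant site can end its AE enquiries before the window in Section 12, 12.2.1 and SAP 5.2.1 closes. Without an EOTV it may make none after the last on-treatment visit. The exposure is confined to late non-serious AEs, including AESIs, and unrelated SAEs. No undercount can be given, because the documents report no post-treatment AE rate and no rate of missed EOTVs.

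The only size available is the scenario figure: up to 24 of 30 days, range 20 to 28. It rests on three assumptions: treatment stops at the scan, AEs are asked about at that visit, and no new systemic therapy starts before Day 30. This is a worthwhile improvement to safety data and does not threaten the trial's main conclusions.

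**What to change.** In 9.11, replace the conditional safety-contact sentence with: *Whether or not an EOTV took place, the site will contact every treated patient on Day 30 (+7 days) after the last study dose and ask about all AEs with onset within the protocol's AE reporting window through Day 30. An EOTV held on Day 30 counts as this contact.*

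Earlier contacts remain allowed, EOTV timing is unchanged, and the early stop in 12.2.1 stays as it is.

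The cost is one sentence. For a patient with an early EOTV, the existing call moves to Day 30. For a patient with no EOTV, one call is added. Some patients will be harder to reach by then because they have moved to other care, so coverage will improve without being complete.
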